7.2 PLANNED ANALYSES

Analysis sets

Statistical analyses will be based on the following analysis sets

- Enrolled set (ES): This subject set includes all subjects having signed informed consent and who were screened for inclusion into the study. The enrolled set will be used for analyses of subject disposition.
- Treated set (TS): The treated set includes all subjects who signed informed consent and were treated with at least one dose of study drug. The treated set will be used for safety analyses.
- Pharmacokinetic parameter analysis set (PKS): This set includes all subjects in the treated set (TS) who provide at least one PK endpoint that was defined as primary and was not excluded due to a protocol deviation relevant to the evaluation of PK or due to PK non-evaluability (as specified in the following subsection ‘Pharmacokinetics’).

Descriptive and model-based analyses of PK parameters will be based on the PKS.

Adherence to the protocol will be assessed by the trial team. Important protocol deviations (iPD) categories will be suggested in the Trial Statistical Analysis Plan (TSAP); iPDs will be

identified no later than in the Report Planning Meeting, and iPD categories will be updated as needed.

Pharmacokinetics

The pharmacokinetic parameters listed in sections [2.2](#) and sections [2.3](#) will be calculated according to the relevant SOP of the Sponsor ([001-MCS-36-472](#)).

Plasma and urine concentration data and parameters of a subject will be included in the statistical pharmacokinetic (PK) analyses if they are not flagged for exclusion due to a protocol deviation relevant to the evaluation of PK (to be decided no later than in the Report Planning Meeting) or due to PK non-evaluability (as revealed during data analysis, based on the criteria specified below). Exclusion of a subject's data will be documented in the CTR. Relevant protocol deviations may be incorrect dose of trial medication taken or use of restricted medications.

Plasma and urine concentrations and/or parameters of a subject will be considered as non-evaluable, if for example

- The subject experienced emesis that occurred at or before two times median tmax of the respective treatment (Median tmax is to be determined excluding the subjects experiencing emesis)
- Missing samples/concentration data at important phases of PK disposition curve

Plasma/urine concentration data and parameters of a subject which is flagged for exclusion will be reported with its individual values but will not be included in the statistical analyses. Descriptive and inferential statistics of PK parameters will be based on the PKS. Only concentration values within the validated concentration range and actual sampling times will be used for the calculation of pharmacokinetic parameters. Concentrations used in the pharmacokinetic calculations will be in the same format provided in the bioanalytical report, (that is, to the same number of decimal places provided in the bioanalytical report).

Biomarkers

Exploratory biomarker endpoints of a subject will be included in the statistical biomarker analyses if they are not flagged for exclusion due to a protocol deviation relevant to the evaluation of biomarkers (to be decided no later than in the Blinded Report Planning Meeting). Exclusion of a subject's data will be documented in the CTR

Relevant protocol deviations may be incorrect dose of trial medication taken or use of restricted medications

7.2.1 Handling of Intercurrent Events

No intercurrent events are defined in this part of the trial.

7.2.2 Primary objective analyses

Primary analyses

The primary endpoints as specified in section [2.2](#) will be calculated according to the BI Standard Operating Procedure(SOP) 'Standards and processes for analyses performed within Clinical Pharmacokinetics/Pharmacodynamics' ([001-MCS-36-472](#)). The analysis will be based on the PKS and will be descriptive in nature.

The statistical model used for the analysis of the primary endpoints will be an analysis of variance (ANOVA) model on the logarithmic scale. That is, the PK endpoints will be log-transformed (natural logarithm) prior to fitting the ANOVA model. This model will include effects accounting for the following sources of variation: 'group', age, and BMI. All effects will be considered as fixed. The model is described by the following equation:

$$y_{km} = \mu + \pi_k + \text{age}_m + \text{BMI}_m + e_{km}, \text{ where}$$

- y_{km} = logarithm of response measured on subject m receiving treatment k,
- μ = the overall mean,
- π_k = the kth group effect, i.e. degree of hepatic impairment, k = 1 for healthy/normal (Group 1), 2 for Group 2 or 3 for Group 3 respectively,
- age_m = the age of the subject m,
- BMI_m = the BMI of the subject m,
- e_{km} = the random error associated with the kth group effect for subject m
- where $e_{km} \sim N(0, \sigma_k^2)$ i.i.d,

Point estimates for the ratios of the geometric means (test/reference) for the primary endpoints (see section [2.2](#)) and their two-sided 90 % confidence intervals (CIs) will be provided.

For each endpoint, the difference between the expected means for log(T)-log(R) will be estimated by the difference in the corresponding adjusted means (Least Squares Means). Additionally, their two-sided 90% confidence intervals will be calculated based on the residual error from the ANOVA and quantiles from the t-distribution. These quantities will then be backtransformed to the original scale to provide the point estimate and 90 % CIs for each endpoint.

Further exploratory analyses

In addition to the model-based approach all parameters will be calculated and analysed descriptively.

7.2.2.1 Sensitivity Analyses

Not applicable.

7.2.2.2 Subgroup Analyses

Not applicable.

7.2.2.3 Supplementary Analyses

Not applicable.

7.2.3 Secondary objective analyses

Not applicable.

7.2.4 Further objective analyses

7.2.4.1 Pharmacokinetic analyses

Further PK endpoints will be analysed descriptively.

7.2.4.2 Biomarker analyses

Biomarker endpoints will be analysed descriptively. The same statistical model as stated in section [7.2.2](#) will be done for further PK endpoints. In addition to the model-based approach all parameters will be calculated and analysed descriptively.

7.2.4.3 Analysis for liquid biopsy

If data allows correlation between CL/F of cocktail components and mRNA or protein expression of respective PK protein in small extracellular vesicle in plasma will be explored outside of this report.

7.2.5 Safety analyses

Adverse events will be coded using the Medical Dictionary for Drug Regulatory Activities (MedDRA). Standard BI summary tables and listings will be produced. All adverse events with an onset between start of treatment and end of the REP, a period of 10 days after trial medication intake, will be assigned to the on-treatment period for evaluation.

All treated patients will be included in the safety analysis. In general, safety analyses will be descriptive in nature and will be based on BI standards. No hypothesis testing is planned.

Statistical analysis and reporting of adverse events will concentrate on treatment-emergent adverse events, i.e., all adverse events occurring between start of treatment and end of the REP. Adverse events that start before first drug intake and deteriorate under treatment will also be considered as 'treatment-emergent'.

Frequency, severity, and causal relationship of adverse events will be tabulated by system organ class and preferred term after coding according to the current version of the Medical Dictionary for Drug Regulatory Activities (MedDRA) at database lock.

Laboratory data will be analysed both quantitatively as well as qualitatively. The latter will be done via comparison of laboratory data to their reference ranges. Values outside the reference range as well as values defined as clinically relevant will be summarised. Treatment groups will be compared descriptively with regard to distribution parameters as well as with regard to frequency and percentage of patients with abnormal values or clinically relevant abnormal values.

Vital signs, physical examinations, or other safety-relevant data observed at screening, baseline, during the trial and at the end-of-trial evaluation will be assessed with regard to possible changes compared to findings before start of treatment.

7.2.6 Other Analyses

No other analyses are planned.

7.2.7 Interim Analyses

No interim analysis planned

7.3 HANDLING OF MISSING DATA

7.3.1 Safety

It is not planned to impute missing values for safety parameters.

7.3.2 Pharmacokinetics

Handling of missing PK data will be performed according to the relevant Corporate Procedure ([001-MCS-36-472](#)). PK parameters that cannot be reasonably calculated based on the available drug concentration-time data will not be imputed.

7.4 RANDOMISATION

This is a non-randomised trial.

7.5 DETERMINATION OF SAMPLE SIZE

No official sample size will be conducted. This is an exploratory study, following numbers of subjects in each of the defined groups:

- **Healthy subjects**
Group 1: 12 healthy subjects
- **Liver cirrhosis patients**
Group 2: 12 F4 Child-Turcotte-Pugh class A (Child-Pugh A) subjects (compensated)
Group 3: 06 F4 Child-Turcotte-Pugh class B (Child-Pugh B) subjects (decompensated)

is fit for purpose.

8. INFORMED CONSENT, TRIAL RECORDS, DATA PROTECTION, PUBLICATION POLICY, AND ADMINISTRATIVE STRUCTURE

The trial will be carried out in compliance with the protocol, the ethical principles laid down in the Declaration of Helsinki, in accordance with the ICH Harmonized Guideline for Good Clinical Practice (GCP), relevant BI Standard Operating Procedures (SOPs), the EU directive 2001/20/EC/EU regulation 536/2014 and other relevant regulations. Investigators and site staff must adhere to these principles. Deviation from the protocol, the principles of ICH GCP or applicable regulations as will be treated as “protocol deviation”.

Standard medical care (prophylactic, diagnostic and therapeutic procedures) remains the responsibility of the treating physician of the patient.

The investigator will inform the sponsor or delegate immediately of any urgent safety measures taken to protect the trial patients against any immediate hazard, as well as of any serious breaches of the protocol or of ICH GCP.

The Boehringer Ingelheim transparency and publication policy can be found on the following web page: trials.boehringer-ingelheim.com. The rights of the investigator and of the sponsor about publication of the results of this trial are described in the investigator contract. As a rule, no trial results should be published prior to finalisation of the Clinical Trial Report.

The certificate of insurance cover is made available to the investigator and the patients and is stored in the ISF.

8.1 TRIAL APPROVAL, PATIENT INFORMATION, INFORMED CONSENT

This trial will be initiated only after all required legal documentation has been reviewed and approved by the respective Institutional Review Board (IRB)/Independent Ethics Committee (IEC) and competent authority (CA) according to national and international regulations. The same applies for the implementation of changes introduced by amendments.

Prior to patient participation in the trial, written informed consent must be obtained from each patient (or the patient's legally accepted representative) according to ICH-GCP and to the regulatory and legal requirements of the participating country. Each signature must be personally dated by each signatory and the informed consent, and any additional patient-information form retained by the investigator as part of the trial records. A signed copy of the informed consent and any additional patient information must be given to each patient or the patient's legally accepted representative.

The patient must be given sufficient time to consider participation in the trial. The investigator or delegate obtains written consent of the patient's own free will with the informed consent form after confirming that the patient understands the contents. The investigator or his delegate must sign (or place a seal on) and date the informed consent form. If a trial collaborator has given a supplementary explanation, the trial collaborator also signs (or places a seal on) and dates the informed consent.

Re-consenting may become necessary when new relevant information becomes available and should be conducted according to the sponsor's instructions.

The consent and re-consenting process should be properly documented in the source documentation.

8.2 DATA QUALITY ASSURANCE

A risk-based approach is used for trial quality management. It is initiated by the assessment of critical data and processes for trial subject protection and reliability of the results as well as identification and assessment of associated risks. An Integrated Quality and Risk Management Plan or alternative plan, in line with the guidance provided by ICH Q9 and ICH-GCP E6, for fully outsourced trials, documents the rationale and strategies for risk management during trial conduct including monitoring approaches, vendor management and other processes focusing on areas of greatest risk.

Continuous risk review and assessment may lead to adjustments in trial conduct, trial design or monitoring approaches.

A quality assurance audit/inspection of this trial may be conducted by the sponsor, sponsor's designees, or by IRB/IEC or by regulatory authorities. The quality assurance auditor will have access to all medical records, the investigator's trial-related files and correspondence, and the informed consent documentation of this clinical trial.

8.3 RECORDS

CRFs for individual subjects will be provided by the sponsor. There is no need for rules about emergency code breaks (see section [4.3.2](#)). For drug accountability, refer to section [4.3.5](#).

8.3.1 Source documents

In accordance with regulatory requirements, the investigator should prepare and maintain adequate and accurate source documents and trial records that include all observations and other data pertinent to the investigation on each trial patient. Source data as well as reported data should follow the "ALCOA principles" and be **attributable, legible, contemporaneous, original, and accurate**. Changes to the data should be traceable (audit trail).

Data reported on the CRF must be consistent with the source data or the discrepancies must be explained.

The current medical history of the patient may not be sufficient to confirm eligibility for the trial and the investigator may need to request previous medical histories and evidence of any diagnostic tests. In this case, the investigator must make at least one documented attempt to retrieve previous medical records. If this fails, a verbal history from the patient, documented in their medical records, would be acceptable.

Before providing any copies of source documents to the Sponsor or designee the investigator must ensure that all patient identifiers (e.g., patient's name, initials, address, phone number, social security number etc) have properly been removed or redacted from any copy of the patients' source documents.

If the patient is not compliant with the protocol, any corrective action e.g., re-training must be documented in the patient file.

For the CRF, data must be derived from source documents, for example:

Proprietary confidential information © 2023 Boehringer Ingelheim International GmbH or one or more of its affiliated companies

- Patient identification: gender, year of birth (in accordance with local laws and regulations)
- Patient participation in the trial (substance, trial number, patient number, date patient was informed)
- Dates of patient's visits, including dispensing of trial medication
- Medical history (including trial indication and concomitant diseases, if applicable)
- Medication history
- Adverse events and outcome events (onset date (mandatory), and end date (if available))
- Serious adverse events (onset date (mandatory), and end date (if available))
- Concomitant therapy (start date, changes)
- Originals or copies of laboratory results and other imaging or testing results, with proper documented medical evaluation (in validated electronic format, if available)
- Completion of patient's participation in the trial" (end date; in case of premature discontinuation document the reason for it).
- Prior to allocation of a patient to a treatment into a clinical trial, there must be documented evidence in the source data (e.g., medical records) that the trial participant meets all inclusion criteria and does not meet any exclusion criteria. The absence of records (either medical records, verbal documented feedback of the patient or testing conducted specific for a protocol) to support inclusion/exclusion criteria does not make the patient eligible for the clinical trial.

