3.3 SELECTION OF TRIAL POPULATION

It is planned that 12 healthy subjects, 12 compensated F4 Child-Pugh A patients and a minimum of 6 decompensated Child-Pugh B patients following clinical confirmation (see section [3.3.2](#) and section [3.3.3](#)) will enter the study. The healthy subjects will be recruited from the volunteers' pool of the trial site. The liver cirrhosis patients will be recruited from a population of patients enriched for disease activity and fibrogenesis. This trial is planned to be conducted without the use of biopsies for either eligibility or efficacy assessments. Thus, the definition of liver cirrhosis and staging will be non-invasive.

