3.3.1 Main diagnosis for trial entry

Please refer to section [8.3.1](#) for the documentation requirements pertaining to the in- and exclusion criteria for:

- **Healthy subjects**
Group 1: 12 healthy subjects
- **Liver cirrhosis patients**
Group 2: 12 F4 Child-Turcotte-Pugh class A (Child-Pugh A) subjects (compensated)
Group 3: 06 F4 Child-Turcotte-Pugh class B (Child-Pugh B) subjects (decompensated)

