Note: subjects with a history of Gilbert syndrome (and hence elevated total bilirubin) are eligible provided that direct bilirubin level \leq ULN, ALT \leq ULN, AST \leq ULN, alkaline phosphatase \leq ULN, haemoglobin \leq ULN, and reticulocyte count \leq ULN

F4 liver cirrhosis patients only

9. Male and female subjects, 18 to 75 years
10. BMI of 18.5 to 40.0 kg/m² (inclusive)
11. Stable treatment for at least 4 weeks prior to taking the cocktail
12. **A)** Patients with compensated liver cirrhosis due to any underlying liver disease with
 13. advanced fibrosis (F4) and hepatic impairment that meets the criteria for Child-Pugh A (see Table [3.3.2: 1](#))
OR
- B)** Patients with decompensated liver cirrhosis due to any underlying liver disease with
 14. advanced fibrosis (F4) and hepatic impairment that meets the criteria for Child-Pugh B (see Table [3.3.2: 1](#))
 - Diagnosis of compensated cirrhosis/F4
 - I. Historic (within 2 years) histological diagnosis of fibrosis stage F4 (NASH-CRN or METAVIR scoring)
 - II. Current or historic increased liver stiffness of \geq 18 kPa by Fibroscan or 5 kPa by MRE
 - OR
 - III. Current or historic imaging of nodular surface with thrombocytopenia $< 150/\text{nL}$
 - OR
 - IV. Clinical signs of portal hypertension (at least one out of the following)
 1. Gastroesophageal varices (GEV)
 2. Splenomegaly (no hematological or infectious diseases, which could cause splenomegaly)
 3. Thrombocytopenia $< 120/\text{nL}$
 - AND
 - V. No previous decompensation events (e.g., ascites, variceal bleeding, hepatic encephalopathy, hepato-renal syndrome)

- Diagnosis of decompensated cirrhosis/F4
 - Any of the above (diagnosis of compensated cirrhosis/F4)
 - AND
 - At least one previous decompensation event

Table 3.3.2: 1 Child-Turcotte-Pugh Scoring Method

Clinical and laboratory criteria	Points ¹		
	1	2	3
Encephalopathy	None	Mild to moderate (Grade 1 or 2)	Severe (Grade 3 or 4)
Ascites	Absent	Slight	Moderate
Bilirubin (mg/dL)	< 2	2–3	> 3
Bilirubin (μmol/L)	< 34.2	34.2–51.3	> 51.3
Albumin (g/dL)	> 3.5	2.8–3.5	< 2.8
Albumin (g/L)	> 35	> 28–35	< 28
Prothrombin time (seconds prolonged) Or INR ²	< 4 < 1.7	4–6 1.7–2.3	> 6 > 2.3

- 1) Child-Turcotte-Pugh class obtained by adding score for each parameter (total score)
 - Child-Turcotte-Pugh A = 5–6 points (mild)
 - Child-Turcotte-Pugh B = 7–9 points (moderate)
 - Child-Turcotte-Pugh C = 10–15 points (severe)

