6.2 DETAILS OF TRIAL PROCEDURES AT SELECTED VISITS

6.2.1 Screening

After having been informed about the trial, all subjects will provide written informed consent in accordance with GCP and local legislation prior to enrolment in the study.

The screening visit includes the following procedures:

- Physical examination (see section [5.2.1](#))
- Examination of vital signs; BP & PR (see section [5.2.2](#))
- Blood draw for safety laboratory tests including a test for viral/bacterial infections, a breath alcohol test (see section [5.2.3](#))
- A urine sample for safety measurements, the drug screening and pregnancy testing in females (see section [5.2.3](#))
- Twelve-lead resting ECG (see section [5.2.4](#))
- Medical examination (see section [5.2.5](#))

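### Section 8.3.1 lets F4 cirrhosis in Group 2 rest on the patient's verbal history, and neither Child-Pugh class A nor the screening procedures reliably catch a patient who does not have it

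*Protocol*

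**What the plan says.** Protocol section 3.3.1 sends the reader to section 8.3.1 "for the documentation requirements pertaining to the in- and exclusion criteria for" the three groups. Section 8.3.1 deals with earlier medical histories and with evidence from diagnostic tests. Where the current history does not settle eligibility, "the investigator must make at least one documented attempt to retrieve previous medical records". It continues: "If this fails, a verbal history from the patient, documented in their medical records, would be acceptable".

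The same section ends with a stricter rule: before allocation, "there must be documented evidence in the source data (e.g., medical records) that the trial participant meets all inclusion criteria". The next sentence, however, counts "verbal documented feedback of the patient or testing conducted specific for a protocol" among the records that can support a criterion, alongside medical records.

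Section 3.3.2 establishes F4 by:
- item I: histology within 2 years;
- item II: stiffness of at least 18 kPa by Fibroscan, or 5 kPa by MRE;
- item III: "Current or historic imaging of nodular surface with thrombocytopenia" below 150/nL;
- item IV: a clinical sign of portal hypertension (varices, splenomegaly, or platelets below 120/nL).

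Group 2 must have had no decompensation and Group 3 at least one event. Each group must also meet its Child-Pugh class: A is 5–6 points, B is 7–9.

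Section 3.3 rules out biopsies for eligibility: "Thus, the definition of liver cirrhosis and staging will be non-invasive". In section 6.2.1, the list headed "The screening visit includes the following procedures" contains physical and medical examination, vital signs, ECG, blood and urine tests and a breath alcohol test.

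**The concern.** Most of the F4 items are test results that a patient can hardly be expected to report accurately, such as a histological stage, a kPa value or an imaging finding. Apart from the platelet count and whatever abdominal palpation shows, no listed trial procedure produces this evidence. If the records cannot be found, the rule allows the diagnosis to rest on what the patient says.

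Study group is the effect of interest in the primary model (protocol 7.2.2, SAP 7.4.1). A patient without F4 who enters Group 2 is analysed as F4 Child-Pugh A and dilutes that contrast, in the direction of concluding that exposure is similar to healthy subjects. No later step in the visible text would show it. A patient admitted under 8.3.1 has complied with the protocol, so no deviation need be raised under SAP 6.2. Protocol 7.2.2.1 to 7.2.2.3 plan no sensitivity, subgroup or supplementary analysis.

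**Working it through.** The plan gives no misclassification or sample-size figure to reproduce. The check has three parts.

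**1. Can a patient without F4 be placed in Group 2?** The minimum Child-Pugh score is 5 items × 1 point = 5, which is class A. The class is therefore no check on F4. Of the items in 3.3.2, screening measures platelets (Table 5.2.3: 1, column A) and examines the abdomen (5.2.1), which may reveal splenomegaly. Platelets below 120/nL or splenomegaly would meet item IV on current data. Otherwise items I to III, or varices under item IV, must come from outside the listed procedures, and 8.3.1 then accepts recall.

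**2. Can the same happen in Group 3?** Class B needs at least 7 points, 2 above the minimum. Bilirubin, albumin and INR are measured at screening; ascites and encephalopathy are the other two items. Recalling a past event supplies none of these points. Only the decompensation event itself can rest on recall.

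**3. Direction and size.** With m of n patients misclassified, equal weights, and age and BMI adjustment ignored:

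expected ratio = exp{[(n − m)·ln(R_group) + m·ln(R_misclassified)]/n}

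Inputs from protocol 1.4.2.3 (rosuvastatin, chronic alcohol liver disease versus normal liver function): Child-Pugh A, Cmax 1.60 and AUC 1.05; Child-Pugh B, Cmax 2.00. Group sizes are 12 and 6. The values of m are assumptions.

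| Case | m = 0 | m = 1 | m = 2 | m = 3 |
|---|---|---|---|---|
| Group 2 Cmax, m patients without F4 (ratio 1) | 1.60 | 1.54 | 1.48 | 1.42 |
| Group 2 AUC, m patients without F4 (ratio 1) | 1.05 | 1.046 | 1.041 | 1.037 |
| Group 2 Cmax, m patients with a forgotten decompensation (ratio 2.00) | 1.60 | 1.63 | 1.66 | 1.69 |
| Group 3 Cmax, m of 6 patients like Child-Pugh A (ratio 1.60) | 2.00 | 1.93 | 1.86 | 1.79 |

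For example, the first row with m = 1 is exp{11·ln(1.60)/12} = 1.54. A ratio of 1 for a patient without F4 is a worst case.

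For scale, the half-width of the 90% interval as a factor is exp{t(0.95; 25)·s·√(1/12 + 1/n)}, with s = √ln(1 + CV²). The residual degrees of freedom are 30 − 3 groups − 2 covariates = 25. With an assumed between-subject CV of 30% to 60% and a common residual variance, the factor is 1.23 to 1.47 for 12 versus 12. Misclassifying one Group 2 patient shifts the Cmax ratio by a factor of 1.60/1.54 = 1.04; three shift it by 1.60^(3/12) = 1.12.

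**The case against.** The route is narrow. It opens only after a documented failed retrieval, and 8.3.1 still wants every criterion supported. A vague recollection would hardly document a stage or a stiffness value. Section 8.3.1 names imaging and test reports as sources for the CRF, and 8.3.2 provides for source verification. Nothing shows that any patient would enter this way. All of this stands and limits the severity. It does not close the gap, because verification would find a documented verbal history, which the section permits.

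Three stronger readings are tempting, and the documents do not support them.

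- *Both patient groups rest on recall.* They do not. Each requires a Child-Pugh class, and the model describes the group effect as degree of hepatic impairment. One healthy-like patient among the six in Group 3 would turn a true ratio of 2.0 into 2^(5/6) = 1.78, but such a patient could not be expected to score 7 points.
- *Misclassification always pulls ratios towards 1.* The third row of the table shows the opposite for a forgotten decompensation in Group 2, if such patients resemble Child-Pugh B.
- *The 2-fold conclusion would often be lost.* With an assumed true ratio of 2.5 and log SD of 0.5 (standard error 0.5·√(2/12) = 0.204), the chance of an estimate above 2 falls from 86% to 49% with three such patients. Neither input is in the documents. With 1.60 and the same SD, the chance is about 14% with none and 10% with one. The synopsis names a 2-fold change as clinically significant, but protocol 7.1 specifies no acceptance range or formal test.

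**Conclusion.** The concern holds for F4 status in Group 2 and, more narrowly, for the decompensation event in Group 3. This is an explicit rule, and the closing sentences of 8.3.1 confirm it. The effect of a patient without F4 in Group 2 is dilution towards 1. For rosuvastatin Cmax that means 1.60 falling to between 1.54 and 1.42 with 1 to 3 of 12 such patients; for AUC the change is negligible. These figures assume healthy exposure in the misclassified patients and apply the protocol's alcohol-related liver disease ratios to this population. The documents give no basis for the number of patients concerned.

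The shift is smaller than the likely half-width of the interval. Unlike sampling error, however, it is a bias that the interval does not reflect. Severity is minor; the case for acting is that the correction is cheap.

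**What to change.** Add to 8.3.1 that the verbal-history fallback does not apply to F4 diagnosis items I to IV of section 3.3.2, nor to the decompensation event required for Group 3. These need a written report (histology, elastography value, imaging, endoscopy, or a hospital or physician letter) or a finding or result obtained at screening. Record in the CRF which item each patient met and its source. Verbal history can remain for the other criteria, including the absence of earlier decompensation in Group 2. A forgotten event there stays possible, but the recorded source makes reliance on recall visible.

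The final SAP is dated 17-MAR-25 and describes some trial conduct in the past tense, so enrolment may be complete. In that case, flag any patient whose F4 or decompensation status rests on verbal history only and repeat the SAP 7.4.1 model without them. If there are none, one sentence in the report settles the matter.

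The cost is a wording change and CRF fields for item and source, with no new procedure. A few patients without retrievable reports would become ineligible, which may slow recruitment slightly.
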